9.3 Description of Screening and Study Design

SCREENING VISIT

After being screened for inclusion/exclusion criteria and providing informed consent, subjects will undergo a complete neurological examination to confirm their diagnosis of ET and exclude other neurological disorders. Additional measures collected during this visit are listed in Appendix 1. Note that subjects will need to have been on a stable dose of their medications for a minimum of 6 weeks prior to the screening visit and will be

encouraged to remain on these doses for the remainder of the study period. Subjects will be asked about their other tremor medication doses at each follow-up visit to confirm stable doses.

VIDEOTAPED TETRAS

As part of each study visit (1-3), subjects will complete a TETRAS rating scale while being videotaped. This is intended for rating purposes by two blinded raters at the completion of the study.

RANDOMIZATION

After completion of the screening visit, subjects will be assigned to one of two possible treatment arms based on a pre-set randomization matrix. Only the research pharmacy who will be responsible for dispensing the doses will be aware of which of two treatment options will be provided, but not the identity of the particular agent. The equivalence of the THC/CBD and Placebo will be equally matched by the manufacturer, making it difficult for the subject to discriminate which arm they are on. Subjects will be asked which arm they are receiving at each assessment visit and on telephone follow up to assess for potential unblinding.

DOSE TITRATION AND TREATMENT

On visit 1 and 5, subjects will receive 1 capsule of IMP every morning. On visit 2 and/or 6, if the subject tolerated 1 capsule then they would receive 2 capsules every morning. Alternatively, if 1 capsule was not tolerated, the timing of the administration would be changed to 1 capsule in the evening. At visit 3 and/or 7, if the single nightly capsule was not tolerated, the subject would be dropped at this visit. If the 2 capsules every morning were tolerated, the subject would then receive 2 capsules in the morning and 1 capsule in the evening. If 2 capsules in the morning were not tolerated, the subject dosing would be changed to 1 capsule in the morning and 1 capsule in the morning and 1 capsule nightly. Subjects will remain on the highest tolerable dose for the duration of the period until visit 4 or 8 (See Appendix 2).

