The starting dose, titration schedule and target dose were selected based on safety, tolerability and efficacy data reported in previous studies using cannabinoids to treat pain (Langford et al., 2013; Portenoy et al., 2012; Johnson et al., 2010). Adverse effects will be inventoried at each study visit. If the patient or investigator feel that the higher study drug dose is causing troublesome side effects, the dosage may be lowered. Food intake can affect systemic exposure of cannabinoids (Zgair et al. 2016). Subjects will be advised to schedule their dose at a similar time every morning after breakfast to maintain similar systemic exposure throughout the study. Regular reminders will be provided to subjects to ensure they are taking the study drug post-meals. During study visits when drug is administered, subjects will be provided with a standardized FDA high-fat, high-calorie meal prior to taking the study drug.

DOSE TAPER AND WASHOUT

After completing a 2-week course on 15/300 mg/day of THC/CBD or placebo, subjects will return on this dose for assessment and completion of the various measures detailed in Appendix 1. After completion of this visit, subjects will taper from the treatment gradually over 1-week, in similar fashion to the dose titration up to the target dose. Subjects will then complete a 3-week washout period prior to being crossed-over to the alternate arm. This is to allow subjects to return to their baselines. The duration selected is conservative and takes into consideration the known elimination half-life of THC/CBD.

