Each patient who consents to participate in the study will receive a copy of the signed and dated written informed consent form and any other information provided to patients prior to the participation in the study. The original signed forms will be maintained in the Investigator's study file. After providing and documenting consent on the IRB approved written informed consent form, patients will be assigned their patient screening number and proceed to the Screening Period.

A copy of the informed consent and HIPAA form has been uploaded for review and approval.

The signed informed consent includes the following information:

- 1. Who is conducting the study
- 2. Procedures
- 3. Potential risks and discomforts
- 4. Benefits
- 5. Expense to subjects
- 6. Confidentiality
- 7. Voluntary participation/withdrawal
- 8. Emergency and study contact
- 9. HIPAA discussion

No study procedures will occur including screening until informed consent is obtained. The patient may withdraw his/her consent to participate in the study at any time. A patient is considered as enrolled in the study when he/she has signed the informed consent form. The entire consenting process will take place in a private exam room to ensure the participant's privacy and confidentiality is protected.

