14. POTENTIAL RISKS

GENERAL ADVERSE EFFECTS

The risks and discomforts known to occur from the use of cannabis include but may not be limited to the following: coordination difficulties, dizziness, lightheadedness, eye irritation, increased heart rate (rapid heart beat), decreased blood pressure (low pressure of blood within arteries), sedation (sleepiness), feeling high, reversible effects on your appetite, mood, memory (ability or recall) and judgment (capacity to form an opinion). Specific mood changes may include anxiety, paranoia, and unusual, disturbing thoughts. Individual response to cannabis varies widely.

DEPENDENCE

Few Cannabis users develop dependence. With prolonged use, individuals may experience withdrawal symptoms such as irritability, restlessness, mild agitation, cramping, nausea, vomiting, sleep disturbances, and loss of appetite. Based on the dose of CBD and THC in TILRAY TN-CT120LM (FDA IND#137400), we do not anticipate symptoms of dependence or withdrawal, but will monitor for them nonetheless.

SOCIAL

Subjects are also informed that THC and CBD can be found in the body days or weeks after exposure, leading to a theoretical risk of a positive drug test should the subject be seeking employment, or undergoes testing as a part of their employment.

CARDIOVASCULAR

While the use of one of the cannabinoids (THC) found in the investigational drug is a rare trigger of cardiovascular events, there may be a significant increase in the rate of cardiovascular events (e.g. heart attack) for 1 hour following the use of cannabis.

REPRODUCTIVE RISKS

While THC and CBD are not known to cause birth defects, the investigators do not wish to expose the unborn child to any unnecessary medications, so subjects who are pregnant or unwilling to use a contraceptive during the course of the study will be excluded. A urine pregnancy test will be performed and confirmed negative before women of childbearing potential may participate in the study.

BLOOD SAMPLING

Since a blood sample will be collected at required study visits, subjects are informed about the risks of pain, discomfort, redness, bruising, infection and/or irritation at the needle insertion site, and rare risks of fainting, dizziness, and lightheadedness that may occur.

QUESTIONNAIRES AND SCALES

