In order to provide independent oversight over patient safety, the PI will select of committee of up to 4 qualified individuals to serve on a Data Safety and Monitoring Board (DSMB). The DSMB will receive regular updates (minimum of quarterly) on adverse events and will have access to unblinded data should they decide to explore whether a frequent or serious adverse event is associated with the study drug. All serious adverse events (SAEs) meeting criteria for expedited reporting to the US FDA will be reported to the FDA, IRB, and DSMB in accordance with regulatory timelines. In the case of a fatal or life-threatening event, we will notify the FDA by telephone within 3 working days and stop further enrollment until the serious adverse event can be reviewed by the DSMB. In addition, any event that is unexpected will be reported to the FDA and IRB within 7 working days.

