APPENDIX 1: STUDY OVERVIEW

EVENT	VISIT 0: SCREENING	VISIT 1: DOSE TITRATION	VISIT 2: PK	VISIT 3: PK	TREATMENT PHASE	VISIT 4: ASSESSMENT	TAPER	WASHOUT	VISIT 5: DOSE TITRATION	VISIT 6: PK	VISIT 7: PK	TREATMENT PHASE	VISIT 8: ASSESSMENT	TAPER	TELEPHONE FOLLOW-UP	TOTAL DAYS
TOTAL DAYS	0	ų	5	1	16	1	5	22	ų	5	1	16	1	5	1	77
DAY NUMBER (±3)	0	1	3	6		22	23	28	50	52	55		71	72	77	
Consent	х															
Neurological Exam	х					x							х			
Vital Signs	х	х	Х	x		х			х	х	x		х			
TETRAS (video)	х					х							х			
Spirography	Х					X							Х			
Accelerometry	Х					Х							Х			
CGI/PGI						Х							Х			
PRO-CTCAE	х	x	х	x		х			x	х	x		х		х	
C-SSRS	Х					Х							Х		Х	
Lab Testing - pregnancy, CBC, CMP, Drug screen	x					x							x			
EKG*	x	x	x	x		x			x	x	x		x			
PK Sample(s)			Х	x		X				x	х		х			

* EKG at screening, then post-dose at each subsequent visit.

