9.16.3 APPENDIX 3: PHARMACOKINETIC SAMPLING TIMES**

DAY #	TIME
3	Trough
6	Trough
22	Trough + Pseudorandom (1,2,3,
	or 4 hrs/post-dose) sample

**NOTE: Samples will be collected for drug and placebo to maintain blinding, but PK lab will be unblinded in order to process only drug samples. If subject receive placebo first, PK days will be: #52, 55, and 71.

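### The pause after a fatal or life-threatening event stops enrollment only, so it does not reach Visit 5, where placebo-first subjects take their first active dose

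*Combined protocol and SAP*

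**What the plan says.** Section 15 sets one automatic pause. After a fatal or life-threatening event the team telephones the FDA and will "stop further enrollment until the serious adverse event can be reviewed by the DSMB". Section 12 defines the term: "A patient is considered as enrolled in the study when he/she has signed the informed consent form".

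The trial is a two-period cross-over. Section 9.3 starts dosing in each period the same way: "On visit 1 and 5, subjects will receive 1 capsule of IMP every morning". Between periods, "Subjects will then complete a 3-week washout period prior to being crossed-over to the alternate arm". Appendix 1 places "VISIT 5: DOSE TITRATION" at day 50 (±3). Appendix 3 says of the blood samples: "If subject receive placebo first, PK days will be: #52, 55, and 71". All three days fall after Visit 5.

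On blinding, section 9.3 states: "Only the research pharmacy who will be responsible for dispensing the doses will be aware of which of two treatment options will be provided". The same sentence adds that the pharmacy does not know which agent is which. Appendix 3 unblinds the PK laboratory, and sections 9.5 and 15 give the DSMB access to unblinded data if it chooses to look.

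**The concern.** An enrollment pause pending DSMB review is there to let the board judge a possible drug harm before more people are exposed. In a parallel-group trial, stopping enrollment does most of that work. In this cross-over, placebo-first subjects meet the drug for the first time at Visit 5, long after they enrolled, and no readable part of the plan holds that visit.

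The protocol itself names an acute risk that would matter here. Section 14 calls THC a rare trigger of cardiovascular events and warns that "there may be a significant increase in the rate of cardiovascular events (e.g. heart attack) for 1 hour following the use of cannabis".

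The site could not easily repair the gap on the spot. Blinded staff cannot pick out the subjects due their first active dose, and the pharmacy knows the treatment option but not the agent's identity.

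**Working it through.** The plan gives no figure to reproduce. The check is mainly textual, with arithmetic only for size.

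**1. Does the pause reach Visit 5?**
- A subject due at Visit 5 has consented, been randomized and taken period 1 capsules. Visit 1 is day 1 and Visit 5 is day 50: 50 − 1 = 49 days earlier. Further enrollment does not describe this person on any reading.
- A placebo-first subject crosses to the other arm at Visit 5, and Appendix 3 places that subject's drug samples on days 52, 55 and 71. Visit 5 is therefore the first active dose.
- The other written stops and dose changes concern the affected individual: withdrawal for suicidality (section 15), and dose changes or drop-out for poor tolerability (section 9.3). None holds other subjects' starts.
- Once the last subject has consented (day 0), the pause stops nothing, although that subject's Visit 5 may be about 50 days away.

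**2. How many first active starts could fall within one review?**

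Inputs from the documents: accrual ceiling 20 and 16 completers (section 9.7), 24 months (section 4), 77 days per subject (Appendix 1), five already enrolled (section 8). Assumed, because the documents do not say: even accrual, 1:1 allocation, and a DSMB review of 7 to 30 days.

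- Gap between subjects: (730 − 77)/19 = 34.4 days.
- Interval between placebo-first Visit 5 starts: 2 × 34.4 = 68.7 days (from the unrounded gap).
- Starts per review: 7/68.7 = 0.10 to 30/68.7 = 0.44.
- If all four spare subjects (20 − 16) drop out before Visit 5, multiply by 16/20 = 0.8: 0.08 to 0.35.
- Counting only the 20 − 5 = 15 subjects still to come, spread over a further 24 months: gap 653/14 = 46.6 days and interval 93.3 days, giving 7/93.3 = 0.08 to 30/93.3 = 0.32. With dropout: 0.06 to 0.26.

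Across these cases the range is 0.06 to 0.44.

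**3. Sensitivity (20 subjects, no dropout)**
- Accrual in 365 days: interval 2 × 365/19 = 38.4 days, giving 0.18 to 0.78.
- Accrual in 180 days: interval 2 × 180/19 = 18.9 days, giving 0.37 to 1.58.
- Placebo-first share of 40% at 24 months: interval 34.4/0.4 = 85.9 days, giving 0.08 to 0.35. Share of 60%: 34.4/0.6 = 57.3 days, giving 0.12 to 0.52.

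**4. What share of first exposures comes at Visit 5?**
- Under 1:1 without dropout, 10 of 20, or half. With the dropout above, 8 of 18, or 44%.
- Among the 15 subjects still to come: 15 × 0.5 = 7.5, or 7.5 × 0.8 = 6.0 with dropout, plus any of the first five not yet crossed over.

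**The case against.** The strongest reply is that Visit 5 is not unprotected. Expedited serious events go to the FDA, IRB and DSMB, and any of these or the investigator could halt dosing. Section 12 requires patients to be told of new information relevant to continuing, with a revised consent form. Section 10.2 excludes significant cardiovascular disorder. Visit 5 starts at one capsule (5 mg THC, Appendix 2), with vital signs and a post-dose EKG (Appendix 1), and section 8 extends each visit to four hours, so the hour named in section 14 falls within a monitored visit. All of this stands and limits the size of the point. None of it is a hold. Discretion to stop enrollment existed too, yet the plan made that pause automatic.

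A second reply is that the remedy draws an arbitrary line. With about 27 days on active drug including taper (days 1 to 28), some 27/34.4 = 0.8 subjects are on active drug at any moment, more than the starts at issue, and these are left to judgement. The line is defensible because the existing pause is about new exposure, and people already on drug need individual decisions on continuing or tapering. It remains a choice.

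Three stronger readings are tempting, and the documents do not support them.
- *The pause also misses Visit 1.* Taken literally, section 12 suggests this for subjects who have consented but not been dosed. But section 9.7 uses the same word for subjects who go on to complete the trial, so a reading that covers Visit 1 is plausible.
- *Only the pharmacy knows the sequence.* The pharmacy is not told the agent's identity, the PK laboratory is unblinded, and the DSMB may be. What holds is that blinded site staff cannot single out first active starts.
- *Subjects would be exposed at every trigger.* Under 24-month accrual the expected number is below one per review.

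**Conclusion.** The point holds as a minor gap in the safety wording. The automatic pause does not cover Visit 5, and followed exactly it would let a placebo-first subject start active drug before the review it exists to secure.

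The size, 0.06 to 0.44 first active starts per review, rests on assumed even accrual over 24 months, 1:1 allocation and a 7- to 30-day review. Faster accrual raises it. It is conditional on an event whose probability the documents do not give. Section 8 reports one adverse effect so far and does not describe it as serious.

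A reader might infer that the trial has no means of holding these subjects. That goes too far: several bodies could act, and a hold rule may exist in the IND letter or Investigator's Brochure (section 25, not supplied) or in the Appendix 2 figure, which is not visible. If one exists, section 15 need only refer to it.

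**What to change.** Keep the trigger and the FDA telephone notice, and replace the final clause of the section 15 sentence with:

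> suspend further enrollment and all first doses of a period (Visit 1 and Visit 5, both sequences) until the event has been reviewed by the DSMB. During the review the investigator and DSMB decide whether subjects already on study drug continue, hold, escalate or taper. Visits delayed by the hold, and later visits of that period, shift by the same number of days and are not window deviations.

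Covering both sequences means that nobody at the site needs unblinding. Visit 1 is named only to remove doubt about the word enrollment. No freeze on up-titration is imposed.

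The cost is one amended and two added sentences unless the trigger fires. If it does:
- Visit 5 starts held per review, both sequences: 7/34.4 = 0.20 to 30/34.4 = 0.87, or 0.16 to 0.70 with dropout (× 0.8). About half are placebo starts, where the hold gains no drug safety.
- The interval from end of taper to Visit 5 grows from 50 − 28 = 22 days to at most 29 (7-day review) or 52 (30-day review).
- Visit 8 moves from day 71 to at most day 78 or day 101. Appendix 1 schedules spirography only at Visits 0, 4 and 8, so period 2 change would be measured against an older screening baseline.
- The hold also applies to events unrelated to the drug, as the present enrollment pause does.

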16. PRIVACY AND CONFIDENTIALITY CONSIDERATIONS INCLUDING DATA ACCESS AND MANAGEMENT

Subjects will be given a Health Insurance Portability and Accountability Act (HIPPA) authorization form to sign. This separate consent will authorize the Investigator(s) and his/her/their staff to access medical records and associated information as may be necessary for purposes of this study. The Investigator and his/her collaborators, staff will consider your records confidential to the extent permitted by law. The Sponsor, Food and Drug Administration (FDA) and Department of Health and Human Services (DHHS) may review these research records. Records may also be reviewed for audit purposes by authorized UCSD employees or other agents who will be bound by the same provisions of confidentiality.

All study-related data will be maintained securely on UCSD computers based on UCSD Information Security policies outlined by the UCSD Administrative Computing and Telecommunications department (ACT). Subjects will receive a study identification number that will only be available to the principal investigator. All other study databases will only include this anonymous study ID number. This anonymous study data may be

maintained indefinitely. Authorized access will only be granted to study investigators or as otherwise defined by university policy. The study site personnel may use this information to notify subjects of appointments, send appointment reminders, or schedule additional appointments.

17. POTENTIAL BENEFITS

Subjects may or may not directly benefit from participating in this study. However, participation may be beneficial to others by providing information that is useful to our understanding of the study drug and its use in ET. The study drug may or may not have any effect on ET.

18. RISK/BENEFIT RATIO

This research represents a more than minimal risk. While there is the limited prospect of direct benefit to individual subjects who could experience a reduction in their tremors, it is more likely to yield generalizable knowledge. All aspects of this research have been designed to limit risk to the extent possible and provides a favorable risk:benefit ratio.

19. EXPENSE TO PARTICIPANT

There will be no cost to subjects to be in this study. Study drug will be provided to subjects free of charge. The study visits, interviews, and examinations during participation will be provided at no cost to subjects. Participants will not be required to pay for parking. Parking permits will be provided by study staff if necessary. The only expense to the participant will be transportation to UCSD.

20. COMPENSATION FOR PARTICIPATION

Subjects will not receive remuneration for participating in this study.

23. FUNDING SUPPORT FOR THIS STUDY

Funding is provided by a grant from the International Essential Tremor Foundation. A contract between Tilray and UCSD will provide study drug and funding for the PK portion of this study.

24. BIOLOGICAL MATERIALS TRANSFER AGREEMENT

N/A

25. INVESTIGATIONAL DRUG FACT SHEET AND IND/IDE HOLDER

See attached FDA IND 137400 Permission to Proceed Letter and Investigator's Brochure.

26. IMPACT ON STAFF

This study will utilize existing resources to conduct this study, including the services of the ACTRI clinic.

27. CONFLICT OF INTEREST

The principal investigator and research have report no conflicts of interest with regard to this study.

28. SUPPLEMENTAL INSTRUCTIONS FOR CANCER-RELATED STUDIES

N/A

29. OTHER APPROVALS/REGULATED MATERIALS

N/A

30. PROCEDURES FOR SURROGATE CONSENT AND/OR DECISIONAL CAPACITY ASSESSMENT

N/A

APPENDIX 1: STUDY OVERVIEW

EVENT	VISIT 0: SCREENING	VISIT 1: DOSE TITRATION	VISIT 2: PK	VISIT 3: PK	TREATMENT PHASE	VISIT 4: ASSESSMENT	TAPER	WASHOUT	VISIT 5: DOSE TITRATION	VISIT 6: PK	VISIT 7: PK	TREATMENT PHASE	VISIT 8: ASSESSMENT	TAPER	TELEPHONE FOLLOW-UP	TOTAL DAYS
TOTAL DAYS	0	ų	5	1	16	1	5	22	ų	5	1	16	1	5	1	77
DAY NUMBER (±3)	0	1	3	6		22	23	28	50	52	55		71	72	77	
Consent	х															
Neurological Exam	х					x							х			
Vital Signs	х	х	Х	x		х			х	х	x		х			
TETRAS (video)	х					х							х			
Spirography	Х					X							Х			
Accelerometry	Х					Х							Х			
CGI/PGI						Х							Х			
PRO-CTCAE	х	x	х	x		х			x	х	x		х		х	
C-SSRS	Х					Х							Х		Х	
Lab Testing - pregnancy, CBC, CMP, Drug screen	x					x							x			
EKG*	x	x	x	x		x			x	x	x		x			
PK Sample(s)			Х	x		X				x	х		х			

* EKG at screening, then post-dose at each subsequent visit.

9.16.2 APPENDIX 2: DOSE TITRATION AND TREATMENT PLAN (THC/CBD*** or PLACEBO)

***Note: THC/CBD formulation will consist of 5mg of THC and 100mg of CBD per capsule.

9.16.3 APPENDIX 3: PHARMACOKINETIC SAMPLING TIMES**

DAY #	TIME
3	Trough
6	Trough
22	Trough + Pseudorandom (1,2,3,
	or 4 hrs/post-dose) sample

**NOTE: Samples will be collected for drug and placebo to maintain blinding, but PK lab will be unblinded in order to process only drug samples. If subject receive placebo first, PK days will be: #52, 55, and 71.
